7.2 Study Conduct

Relevant protocol deviations, which could have major impact on the interpretation of the primary efficacy endpoint of the study results, will be identified prior to the unblinding the database for all subjects who are randomized and receive double-blind medication. Relevant protocol deviation criteria are listed in [APPENDIX 1](#).

All relevant protocol deviations, pre-randomization and during double-blind period, will be listed and summarized by treatment arm. The per-protocol analysis population will exclude subjects with at least 1 relevant protocol deviation. Relevant protocol deviations will not be assessed for the OLE analysis.

7.3 Study Population

Summary statistics of data pertaining to subject disposition, demographics, baseline characteristics, and medical history will be tabulated and displayed by randomized treatment arm. No statistical test will be carried out for comparison of any baseline measurement among treatment groups.

7.3.1 Subject Disposition

The number of subjects enrolled into the study, and the number of subjects enrolled but not randomized together with the reasons for not being randomized will be summarized. The reasons for not being randomized will be taken from the CRF pre-randomization status page.

Enrollment at each site and by age group (adult and pediatric) will be summarized as specified in EudraCT requirements.

The disposition of subjects during the double-blind period will include the number of subjects randomized, the number of subjects who are randomized and treated, the number of subjects who are randomized but not treated, the number of subjects who complete the double-blind period and the number of subjects who discontinue the double-blind period together with the reasons for discontinuation.

For subjects who completed Period 1 and entered Period 2 prior to the protocol revision, the number of subjects who complete Period 2 and the number of subjects who discontinue the Period 2 together with the reasons for discontinuation will be summarized.

The number of subjects who enter the OLE, the number of subjects who complete the OLE and the number of subjects who discontinue the OLE together with the reasons for discontinuation will be summarized.

7.3.2 Demographic and Baseline Disease Characteristics

Demographic and baseline disease characteristics will be summarized using the ITT Analysis Population for pediatric patients (< 18 y), adult patients (≥ 18 y) and overall in separate summaries. Continuous variables will be summarized using means and standard deviations, and categorical variables will be summarized using frequency distributions. Summaries will be presented by randomized treatment group.

The following demographic and baseline characteristics will be summarized:

- Age
- Age group (18 - 64 y, ≥ 65 years for adults and 6 -< 18 y for pediatric subjects)
- Gender
- Race
- Ethnicity
- Weight by age group (pediatric and adult)
- Weight group (< 60, 60 - 100, > 100kg for adult and < 75, 75 - 100, > 100kg for pediatric)
- Height (pediatric only)
- BMI
- Randomization Strata (APOL1 high risk group vs. Others)
- Serum albumin at baseline (g/dL)
- Estimated Glomerular Filtration Rate at baseline (mL/min/1.73m²)
- Urine protein/creatinine ratio at baseline (mg/mg)
- Diagnosis (FSGS versus MCD)

7.3.3 Medical History and Prior Medication

General medical history will be summarized by each body system for the ITT Analysis Population.

Prior medications are defined as medications a subject started to take prior to the first infusion of double-blind study medication. Prior medications will be summarized for each treatment arm by drug class and generic name for the ITT Analysis Population.

Medications of special interest to TRNS (FSGS/MCD) include corticosteroids (CS) (prednisone or equivalent), calcineurin inhibitors (cyclosporine and tacrolimus), sirolimus, mycophenolate mofetil (MMF), mycophenolic acid (MPA), or cyclophosphamide. A summary of prior medications of special interest will be provided for each treatment group.

7.4 Extent of Exposure

7.4.1 Study Therapy

Extent of exposure to double-blind study drug will be summarized using the As Treated Analysis Population in two ways:

- Number of infusions.
- Number of days a subject is known to be on study drug ignoring dosing interruptions.

The number of infusions subjects received will be based on the study medication page of the CRF when an infusion date is present.

The number of days the subject is known to be on study drug (exposure to study drug) during each period is calculated as:

Double-blind period:

- Discontinued subjects during double-blind period and subjects completed double-blind period but do not continue into the OLE:

Exposure in days = (date of last study medication in the double-blind period - date of first study medication in the double-blind period + 1) + 56.

- Subjects continuing in the OLE:

Exposure in days = (date of first study medication in OLE - date of first study medication in double-blind period) - adjustment.

Adjustment is the period after 56 days from last study medication from double-blind period to the first study medication in OLE.

- Subjects who completed Period 1 and entered Period 2 prior to the protocol revision:

Exposure = (date of first study medication in Period 2 - date of first study medication in Period 1) - adjustment.

Adjustment is the period after 56 days from last study medication from Period 1 to the first study medication in Period 2.

OLE period:

Exposure = (date of last study medication in OLE - date of first study medication in OLE + 1) + 56.

Cumulative abatacept safety period:

- Subjects treated with abatacept and discontinuing before entering the OLE:

Exposure in double-blind period = (date of last study medication in double-blind period - date of first study medication in double-blind period + 1) + 56.

- Subjects treated with abatacept and continuing in the OLE, it is the sum of the following:

Exposure in double-blind period = (date of first study medication in OLE - date of first study medication in double-blind period) - adjustment.

Exposure in OLE = (date of last study medication in OLE - date of first study medication in OLE + 1) + 56.

For subjects randomized to placebo, the date of first abatacept study medication is the date of first study medication in OLE. For subjects randomized to abatacept, the date of first abatacept study medication is the date of first double-blind period.

- Subjects who completed Period 1 and entered Period 2 prior to the protocol revision:
 - For subjects on abatacept during Period 1 and entering OLE period, it is the sum of the following:
 - ◆ Exposure in Period 1 = (date of first study medication in Period 2 - date of first study medication in Period 1 + 1) + 56.
 - ◆ Exposure in OLE = (date of last study medication in OLE - date of first study medication in OLE + 1) + 56.
 - For subjects on abatacept during Period 2, it is the sum of the following:
 - ◆ Exposure in Period 2 = (date of first study medication in OLE period - date of first study medication in Period 2) - adjustment. Adjustment is the period after 56 days from last study medication from Period 2 to the first study medication in OLE.
 - ◆ Exposure in OLE = (date of last study medication in OLE - date of first study medication in OLE + 1) + 56.
 - For subjects on abatacept during Period 2 and not entering OLE:
 - ◆ Exposure in Period 2 = (date of last study medication in Period 2 - date of first study medication in Period 2 + 1) + 56.

The offset of 56 days is the length of 2 regular dosing cycles and represents approximately 4 times the half-life of abatacept in humans.

Summaries of exposure to study drug will show the distribution of the number of infusions and days on drug, together with the means, standard deviations, medians, minima and maxima, by treatment group.

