3.6 Post Study Drug Study Follow up

Subjects who discontinue study drug may continue to be followed.

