Table 5.1-3: Open Label Extension								
Visit Day (± 7 days)	Day 1 (Same day as last visit of the Double Blind Period)	Day 29	Day 57	Day 85	Day 113	Day 141	Day 169 or Early Termination	Notes
Contact Central Randomization System	X	X	X	X	X	X	X	
Safety Assessments								
Adverse Event Monitoring		X	X	X	X	X	X	
████████████████████		█	█	█	█	█	█	
Targeted Physical Exam		X	X	X	X	X	X	
Weight		X	X	X	X	X	X	
Vital Signs		X	X	X	X	X	X	Seated BP, heart rate, temperature should be taken pre-dose and 60 minutes post-dose.
██████████		X	X	X	X	X	X	████████████████████
Emergency Room/Hospitalization CRF		X	X	X	X	X	X	
Laboratory Assessments								
CBC							X	
Chemistry panel			X		X		X	
Total Cholesterol and Triglycerides, fasting							X	
Urine sample for protein/creatinine ratio		X	X	X	X	X	X	To be taken from a single voided specimen. Morning collections are preferred.
eGFR							X	
Urine pregnancy test		X	X	X	X	X	X	Testing performed locally on WOCBP subjects only

Table 5.1-3: Open Label Extension								
Visit Day (± 7 days)	Day 1 (Same day as last visit of the Double Blind Period)	Day 29	Day 57	Day 85	Day 113	Day 141	Day 169 or Early Termination	Notes
Clinical Supplies								
Drug preparation by a pharmacist	X	X	X	X	X	X		
Abatacept dosing	X	X	X	X	X	X		

Table 5.1-4: Follow-Up Visits (after last dose)^a				
Visit (± 14 days)	56 Days after Last Dose	84 Days after Last Dose	168 Days after Last Dose	Notes
Adverse Event Monitoring	X	X	X	
████████████████████	■	■	■	
Targeted Physical Exam	X	X	X	
Vital Signs	X	X	X	Seated BP, heart rate, temperature
Emergency Room/Hospitalization CRF	X	X	X	
Laboratory Assessments				
Urine pregnancy test	X	X	X	Testing performed locally on WOCBP subjects only
Immunogenicity anti-abatacept Ab testing	X	X	X	
Pharmacokinetic Sampling in Blood	X	X	X	The sample will be stored until a decision is made that the testing will be needed.

^a Testing will be required only if the subject is off abatacept treatment and does not transition to commercially available treatment with abatacept.

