7.6.3 Incidence Rate Analyses

Incidence rate is defined as the quotient of number of subjects with event and exposure (patient-years), where the exposure (patient-years) is the sum over all subjects' exposure during a pre-specified study period (censored at the time of the first occurrence of event) divided by 365. The resulting incidence rate is multiplied by 100 to express the rate per 100 p-y. Incidence rates per 100 p-y and associated 95% Poisson confidence intervals will be calculated for each treatment group.

Incidence rate analyses will be performed for SAEs, Renal Related AEs, Opportunistic Infections, Malignancy and Autoimmune disorders, the point estimate and 95% CI of incidence rate (per 100 patient-years) of each endpoint will be provided by system organ class and preferred term, separately for each treatment group.

The analyses will be performed for events that occurred in double-blind period up to 56 days post last dose in double-blind period or first dose date in OLE whichever is earlier.

For subjects who completed Period 1 and entered Period 2 prior to Protocol Amendment 2, the analyses will be performed for events that occurred in Period 1 up to the first dose in Period 2.

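### Double-blind incidence rates count 56 days after the last dose even for subjects no longer observed, which can only lower the rates

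*SAP*

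**What the plan says.** SAP 7.4.1 introduces its formulas with "The number of days the subject is known to be on study drug (exposure to study drug) during each period is calculated as". It then treats two groups in the double-blind period differently.

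- **Subjects who discontinue, or complete but do not enter the OLE:** "Exposure in days = (date of last study medication in the double-blind period", less the date of "first study medication in the double-blind period + 1) + 56".
- **Subjects who continue into the OLE:** first OLE dose minus first double-blind dose, less an adjustment: "Adjustment is the period after 56 days from last study medication from double-blind period to the first study medication in OLE". Here 56 days is an upper limit on the gap, not an addition. Subjects who moved from Period 1 to Period 2 under the old design are handled the same way.

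The OLE formula is "Exposure = (date of last study medication in OLE - date of first study medication in OLE + 1) + 56".

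SAP 7.6.3 divides the number of subjects with an event by summed exposure "during a pre-specified study period (censored at the time of the first occurrence of event". Those rates cover the double-blind period only, up to 56 days after its last dose or the first OLE dose. SAP 7.6.4 also reports rates for the OLE and cumulative periods, but takes exposure from sponsor standard algorithms that the SAP does not reproduce.

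Protocol 3.1.4 and Table 5.1-4 plan three visits, the first 56 days after the last dose. Footnote a of that table limits them: "Testing will be required only if the subject is off abatacept treatment and does not transition to commercially available treatment with abatacept".

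**The concern.** A rate is interpretable only if its denominator is time during which an event would have been recorded. The 56 days are added whatever happened to the subject after the last dose. No formula ends at death, withdrawal of consent, loss to follow-up or data cutoff, although the quantity is described as known time. The SAP already accepts the principle for continuing subjects, whose clock stops at the next period's first dose. It does not extend it to the end of observation.

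The error runs in one direction: unobserved event-free time makes the drug or the placebo look safer. If discontinuation or OLE entry differs between arms, the understatement differs too. The rates concerned are for serious, renal-related, opportunistic-infection, malignancy and autoimmune events, in a study of about 90 subjects with little person-time.

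A second gap concerns timing. The double-blind analysis starts once every subject has reached Day 113 or discontinued (SAP, Schedule of Analyses), while a non-continuer's safety window runs to about Day 141. SAP Table 9-2 places the double-blind tables in the first report only. The cumulative period in SAP 6.1 starts at the first abatacept dose, so a placebo subject who never enters the OLE under the current design is outside it. An event in such a subject after the cutoff but inside the window could miss the between-arm tables.

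**Working it through.** **The plan's own figures.** The worked rate in SAP 7.6.4 reproduces: 7/20 × 100 = 35 per 100 patient-years. So does the basis for the offset: 2 × 28 = 56 days. With 5 half-lives equal to 70 days (Protocol 3.3.1), the half-life is 14 days, and 56/14 = 4.

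**Inputs.** Double-blind doses are on Days 1, 15, 29, 57 and 85 (Protocol 4.5.2). OLE doses run to OLE Day 141 (Protocol 4.5.3), and the last OLE visit is Day 169 (Protocol Table 5.1-3). Formulas are from SAP 7.4.1, applied to planned dates.

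**Per subject: credited against observed.**

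- Continues into the OLE: 113 − 1 = 112 days credited; no excess.
- Non-continuer, last dose Day 85, seen at the 56-day visit: (85 − 1 + 1) + 56 = 141 credited; no excess.
- Same subject, observed only to Day 113: 141 credited, 113 observed. Excess 28 days; 28/141 = 19.9% low for that time.
- Lost on the day of the first dose: (1 − 1 + 1) + 56 = 57 credited, 1 observed. This is the largest possible excess, 56 days.
- OLE completer with no follow-up visits: (141 − 1 + 1) + 56 = 197 credited, 169 observed. Excess 28 days; 28/197 = 14.2%.

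**Arm level, double-blind.** The documents give no dropout or OLE-entry figure, so these are assumptions: 80% continue (112 days each); a share f of the arm is not observed for the last u days of its credited time; the rest are non-continuers followed in full (141 days). Event-free time only is considered.

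With L the day of the last dose in the unobserved group:

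mean credited days = 0.80 × 112 + f × (L + 56) + (0.20 − f) × 141

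understatement = f × u / mean credited days

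- f = 5%, u = 28, L = 85: mean 117.8; 1.4/117.8 = 1.2%.
- f = 10%, u = 56, L = 85: mean 117.8; 5.6/117.8 = 4.8%.
- f = 20%, u = 56, L = 85: mean 117.8; 11.2/117.8 = 9.5%.
- f = 20%, u = 56, L = 29: mean 89.6 + 17.0 = 106.6; 11.2/106.6 = 10.5%.
- f = 0: no bias.

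**Unequal arms, for illustration.** With u = 56 and L = 85, one arm at f = 5% is 2.8/117.8 = 2.4% low and the other at f = 20% is 9.5% low. The rate ratio between arms is then off by a factor of 0.976/0.905 = 1.08.

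**The case against.** The strongest reply is that observation through the window is planned. Table 5.1-4 has a visit with adverse event monitoring 56 days after the last dose. Protocol 3.5 and 3.6.1 expect subjects who stop drug to stay in follow-up unless they withdraw consent or lose the ability to consent freely, and Protocol 6.1.1 requires serious events to be collected for 6 months after dosing stops. The 56 days also match the event window in SAP 6.1 and 7.6.3. As a measure of drug exposure, the formula is coherent. No between-arm test of event frequencies is planned.

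Most of this stands, and it limits the size of the problem. It does not remove it. Withdrawal of consent, death and loss to follow-up still occur, and Protocol 3.6 is weaker than 3.6.1: "Subjects who discontinue study drug may continue to be followed". Matching the event window does not help when no event could have been recorded in it.

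A reader might infer three stronger things that the documents do not support.

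- *That 56 days are always added.* They are not: continuing subjects are cut at the next period's first dose.
- *That cumulative rates are about 14% low for subjects randomized to placebo (28/197) and 9% low for those randomized to abatacept (28/(112 + 197) = 28/309).* These are per-subject worst cases. They require every subject to complete the OLE and go unobserved after Day 169. They also require the 7.6.4 rates to use the 7.4.1 formula, which cannot be confirmed. The OLE formula does not enter the 7.6.3 rates at all.
- *That late events generally disappear.* Only non-continuers whose last dose fell within 56 days of the cutoff are exposed to this, and the listings of adverse events of interest run to database lock.

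**Conclusion.** The point holds for double-blind subjects who discontinue or do not enter the OLE. As written, their person-time includes 56 days after the last dose whether or not they were observed, so the 7.6.3 rates can only be biased downward, and unequally if the arms differ in discontinuation or OLE entry. The size is 28 days (19.9% of credited time) for a non-continuer seen only to Day 113. At arm level it is roughly 1% to 10% under the assumed 80% OLE entry and 5% to 20% of the arm unobserved for 28 to 56 days. It is zero if everyone is followed to day 56.

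This reads 7.6.3 as using the 7.4.1 formulas, the only exposure definition the SAP states. The OLE formula has the same gap, but its effect on any reported rate is unknown. The cutoff gap is real but narrow. It matters most for placebo subjects who never enter the OLE, because no later summary period includes them.

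**What to change.** In SAP 7.6.3, and in 7.6.4 wherever 7.4.1 exposure is used, keep censoring at the first event and otherwise end person-time at the earliest of:

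- last dose + 56 days;
- death;
- withdrawal of consent or last contact;
- data cutoff;
- first dose of the next period (already applied to continuing subjects).

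State in 7.6.4 whether the sponsor algorithms follow the same rule. The exposure summaries in 7.4.1 may stay as they are, since they describe drug exposure rather than observation time.

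Repeat the double-blind safety tables in the end-of-study report and add them to Table 9-2. This completes the 56-day window for non-continuers whose window ran past the first cutoff, in particular placebo subjects who never enter the OLE.

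The cost is one definition, one repeated set of tables and slightly higher rates. The protocol schedule does not change.

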Eligibility will be based on specified inclusion and exclusion criteria, medical history, disease activity and safety assessments. Randomization should occur within 28 days of signing the informed consent. This may be extended to 42 days to allow for screening results (eg, TB, *APOL1* SNP, UPCR and eGFR).

3.1.2 Double-Blind Period (Day 1 - Day 113):

On Day 1, subjects will be randomized to one of two blinded parallel treatment arms in a 1:1 ratio:

Abatacept IV

adults use weight-tiered dose:

< 60 kg:	500 mg
60 to 100 kg:	750 mg
> 100 kg:	1000 mg

pediatric patients 6 to 17 years:

< 75 kg:	10 mg/kg
≥ 75 kg	follow adult dosing.

Placebo (Normal Saline or D5W following the same dosing schedule).

Dosing is on Day 1, 15, 29, and then every 28 days.

The duration of the Double-Blind Period is 113 days.

There is an option to Early Escape into the OLE on Day 85 for pediatric age subjects only (< 18 years of age at randomization). The decision to Early Escape will be based on the Day 57 UPCR (> 3) and the assessment of clinical status on Day 85. If at the discretion of the investigator, in consultation with the subject (and their guardians), it is decided that the subject's clinical status has worsened or not improved sufficiently based on both of these criteria, the Day 85 visit may be skipped. The subject would complete the Double-Blind Period Early Termination visit ([Table 5.1-2](#)). The decision will then be made to either proceed to the OLE Day 1 visit ([Table 5.1-3](#)) or the Follow-up Visits ([Table 5.1-4](#)).

3.1.3 Open Label Extension (Day 1 - Day 169):

At the end of the Double Blind, there will be a 169 day open label extension (OLE). Subjects may enter this extension in 2 different manners. Subjects who reach the end of Double Blind will be able to volunteer to enter the OLE at the discretion of the investigators. Pediatric age subjects (6 to 17 years) who choose to Early Escape may then choose to enter the OLE. This includes both responder and non-responders who wish to determine if a longer exposure to abatacept could lead to a response. Abatacept will be administered every 28 days starting on Day 1 of the OLE (Day 1 of the OLE will be Day 113 of the Double Blind Treatment Period), without a loading dose. Adjustment in background therapy is allowed but limited. This includes increases or decreases in doses, including discontinuation, or change from one permitted agent to another (3.4.1.2, Restricted Treatments During Double-Blind).

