- Double-blind period analysis: This analysis will be performed for the double-blind period when all subjects complete their Day 113 visit assessment or discontinue prematurely prior to Day 113. At the time of the first analysis the data will be unblinded. This analysis will include primary endpoint and secondary endpoints.
- End of study analysis: A second analysis will be performed at the end of the study when all subjects complete their open label extension (OLE) and follow-up period or discontinue prematurely.

This statistical analysis plan will describe the analysis to be performed at the end of the double-blind period and at the end of the study.

Prior to Protocol Amendment 2, the study design had a blinded-study drug period that was twice as long as the current double-blind period and was divided into 2 periods of equal length, known as Period 1 and Period 2, so that randomized subjects could switch blinded therapy. The current design eliminates Period 2 and renames the previous Period 1 as the double-blind period.

This modification does not impact the primary nor secondary study objectives. It does impact the exploratory objectives which addressed persistence of response and onset of response during Period 2, these are now eliminated.

For subjects who completed Period 1 and entered Period 2 prior to the protocol revision, the Period 1 data will be analyzed as part of the double-blind period since study execution during this timeframe is unchanged, the Period 2 data will only be listed. Period 2 data won't be part of any summaries except for safety summaries at the end of the study on the cumulative abatacept safety period.

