2 STUDY DESCRIPTION

2.1 Study Design

This is a phase II randomized, placebo-controlled, double-blind, parallel arm design study to evaluate the efficacy and safety of intravenous abatacept in treatment resistant nephrotic syndrome (Focal Segmental Glomerulosclerosis / Minimal Change) in adult and pediatric subjects.

This pilot study will randomize approximately 90 subjects 1:1 to intravenous (IV) abatacept or placebo in a double-blind (DB) fashion. The randomization will be stratified by Genotype for whom test results, obtained either prior to enrollment or at screening, are available (APOL1 high risk group vs. Others) and Age (< 18 y and ≥ 18 y).

The trial will consist of 4 periods: the screening period will be 28 days (can be extended an additional 14 days to complete testing by repeating screening labs), a 16 week double-blind treatment period (parallel arms: IV abatacept vs. IV placebo), a 168 day abatacept open label extension period (OLE), and a 6 month follow-up period.

Subjects randomized to abatacept treatment in the double-blind period will be dosed as follows. Adults will use the weight-tiered dose: < 60kg: 500mg, 60 to 100kg: 750mg, > 100kg: 1000mg;

pediatric patients 6 to 17 years who weigh < 75kg will receive:10mg/kg and those who weigh \geq 75kg will follow adult dosing. Dosing is on Day 1, 15, 29, 57, 85. Subject in the placebo arm will receive normal Saline or D5W following the same dosing schedule. In the OLE, subjects who enter will all receive age and weight-based IV abatacept every 28 days for 169 days.

The primary efficacy assessment, renal response (defined in [Section 8.1.1](#)), will be on Day 113. On Day 113, all subjects who choose to receive open label therapy with abatacept will enter the OLE. During the OLE, the durability (i.e., continuity of response) and stability (i.e., the change in urine protein/creatinine ratio (UPCR)) of response will be determined by continuing to capture and describe the same study outcomes among responders. Adjustment of background therapy will also be allowed during the OLE at the discretion of the investigators and subjects to determine the relative contribution (or need) of these agents for renal responses.

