6 STUDY PERIODS, TREATMENT REGIMENS AND POPULATIONS FOR ANALYSES

6.1 Study Periods

In this study, there are four study periods: screening period, double-blind period (DB), open label extension period (OLE), and follow-up period.

The following analysis periods defined below are for analysis purposes. The definitions below indicate the data to be included in the analysis of each specified period. Subjects discontinued during a specified period (DB or OLE) will be considered on-treatment for 56 and 42 days after the last dosing in that period for safety and efficacy analysis respectively. Follow-up period data will be included in one of the analysis periods depending on the time of completing the study.

Screening Period: Starts with the day of enrolment and ends prior or on the day of first dose of study medication (abatacept or placebo).

Double-Blind Period: Starts with the first dosing of double-blind study medication and ends 56/42 days (for safety/efficacy analysis) after the last dose of the double-blind period or the first dosing of OLE, whichever is earlier.

For subjects who completed Period 1 and entered Period 2 prior to Protocol Amendment 2, includes data from first dose date in Period 1 up to the first dose in Period 2.

Open Label Extension Period (OLE): Starts with the first dosing in the OLE and ends 56/42 (for safety/efficacy analysis) days after the last dose in the OLE.

Cumulative Abatacept Safety Period: Starts at the time of the first dose of abatacept (either in the double-blind period for the subjects randomized to abatacept or in the OLE for the subjects randomized to placebo) and continues up to 56 days post last dose of abatacept for safety (AE and laboratory summaries). The last abatacept dose can be last dose in double-blind period for subjects not treated in the OLE.

For subjects who completed Period 1 and entered Period 2 prior to the protocol revision:

- For subjects on abatacept during Period 1:
 - For subjects who do not enter OLE period: starts with the first dosing of Period 1 and ends 56 days after the last dosing of Period 1.
 - For subjects who enter OLE period: starts with the first dosing of Period 1 and ends 56 days after the last dosing of Period 1 combined with OLE period that starts with the first dosing in the OLE period and ends 56 days after the last dosing in the OLE period.
- For subjects on placebo during Period 1:

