7.6.4.1 EudraCT Summaries

Exposure adjusted adverse event summaries including multiple occurrences of unique adverse events for EudraCT reporting requirements will be presented by treatment group in the cumulative abatacept safety period. These summaries include serious adverse events, drug related serious adverse events and non-serious adverse events using a global cutoff of 5 percent.

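### For legacy subjects on abatacept in Period 1 who entered the OLE, the SAP 7.4.1 exposure formula overruns the period defined in SAP 6.1, nominally by 28 days

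*SAP*

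**What the plan says.** Before Amendment 2 the blinded part of the trial had two equal periods, and subjects could switch treatment at the second. The SAP introduction keeps the Period 1 data: "the Period 1 data will be analyzed as part of the double-blind period since study execution during this timeframe is unchanged". Period 2 data enter only the end-of-study safety summaries for the cumulative abatacept safety period.

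For subjects on abatacept in Period 1 who later entered the OLE, SAP 6.1 (Cumulative Abatacept Safety Period) defines a period that "starts with the first dosing of Period 1 and ends 56 days after the last dosing of Period 1 combined with OLE period", the OLE segment running to 56 days after its own last dose.

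SAP 7.4.1 (cumulative abatacept safety period, legacy subjects) gives the exposure formula for the same subjects. The Period 1 term is ("date of first study medication in Period 2 - date of first study medication in Period 1 + 1) + 56", and a separate OLE term is added.

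The remaining formulas in 7.4.1 take one of two forms:

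- **Last dose plus tail.** An example is ("date of last study medication in the double-blind period - date of first study medication in the double-blind period + 1) + 56", for subjects who do not go on to the OLE.
- **First dose of the next period.** No 56 days are added, and any time beyond 56 days after the last dose is subtracted as an adjustment. Four formulas have this form: double-blind exposure of subjects continuing to the OLE, double-blind exposure of legacy subjects, the double-blind part of cumulative exposure for abatacept subjects continuing to the OLE, and Period 2 exposure of legacy subjects who had abatacept there and entered the OLE.

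**The concern.** The quoted line takes its end date from the second form and its 56-day tail from the first, and neither form alone produces it. The SAP explains the 56 days as two dosing cycles, about four half-lives of abatacept. That makes it a tail after the last abatacept dose. In this line the tail starts instead at the first Period 2 dose, which for these subjects appears to be placebo.

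The line feeds the cumulative exposure summary that SAP 9 places in the end-of-study report. If the same exposure also serves as the denominator of cumulative-period event rates, the extra days carry no matching events, because they lie outside the period that 6.1 defines. Those abatacept rates would then be too low, which is the unwelcome direction for safety reporting.

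**Working it through.** **Inputs**

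- Period 1 doses: "Dosing is on Day 1, 15, 29, 57, 85" (SAP 2.1). The first dose is Day 1 and the last is Day 85. They apply to legacy subjects because the SAP introduction says Period 1 was conducted in the same way.
- First Period 2 dose: Day 113. This is inferred. The Protocol says "The duration of the Double-Blind Period is 113 days" (3.1.2), the SAP introduction describes two periods of equal length, and SAP Table 8.6-2 places the next visits after Day 113 at Days 128 and 141.
- Treatment in Period 2: placebo for subjects who had abatacept in Period 1. This is inferred from the switch described in the SAP introduction, and from SAP 6.1, which starts abatacept time for Period 1 placebo subjects at their first Period 2 dose.
- OLE doses: OLE Days 1 to 141 (Protocol 4.5.3).

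**The plan's own figure.** The 56-day offset reproduces. Two cycles give 2 × 28 = 56. The contraception criterion in Protocol 3.3.1 equates 5 half-lives with 70 days, so one half-life is 70 / 5 = 14 days and 4 × 14 = 56.

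**Period 1 segment on the nominal schedule**

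| Rule | Calculation | Days | Last day covered |
|---|---|---|---|
| SAP 7.4.1 as written | (113 − 1 + 1) + 56 | 169 | Day 169 |
| SAP 6.1 definition | (85 − 1 + 1) + 56 | 141 | Day 141 |

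The excess is 169 − 141 = 28 days (Days 142 to 169), and 28 / 141 = 19.9%.

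**With a full OLE course.** The OLE term is (141 − 1 + 1) + 56 = 197 days. The totals are 169 + 197 = 366 and 141 + 197 = 338 days, and 28 / 338 = 8.3%.

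**General form.** [(first P2 − first P1 + 1) + 56] − [(last P1 − first P1 + 1) + 56] = first P2 − last P1. The excess is therefore each subject's actual gap between those two doses, and it is always positive. If each dose can move by 7 days (Protocol 4.5.2 for Day 85; assumed for Period 2), the gap runs from 106 − 92 = 14 to 120 − 78 = 42 days. If the Day 85 dose was missed and Day 57 was the last, it is 113 − 57 = 56 days.

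**Aggregate, for illustration only.** Assume 45 subjects per arm who all complete the OLE, counted by the current-design formulas. Cumulative exposure is then 45 × (112 + 197) + 45 × 197 = 22,770 days, where 112 = 113 − 1. Each affected subject adds 28 / 22,770 = 0.12%. Five add 140 / 22,770 = 0.6%, and fifteen add 420 / 22,770 = 1.8%. Lower enrolment or OLE dropout would raise these shares.

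**The case against.** The strongest reply accepts the mismatch and disputes its reach. Most of that reply stands.

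- **Adverse event rates.** A reader might infer that the abatacept event rates are understated. The documents do not establish this. The SAP 7.6.3 incidence rates for legacy subjects stop at the first Period 2 dose. For multiple-occurrence rates, SAP 7.6.4 refers exposure to standard sponsor algorithms that are not reproduced. The EudraCT summaries, which "will be presented by treatment group in the cumulative abatacept safety period", sit under that section. Whether either uses the 7.4.1 line is unknown.
- **An isolated departure from one rule.** A reader might infer that every other formula in 7.4.1 is last dose plus 56. Four are not. The line is wrong because it joins two valid forms and disagrees with 6.1.
- **56 days of placebo time.** A reader might count the whole tail after Day 113 as error. SAP 6.1 itself allows the tail to run into Period 2 as far as Day 141, so the nominal excess is 28 days.
- **An uncapped tail.** A reader might add that the 56 days should stop at death or last contact. The fixed offset is a stated convention, and SAP 7.6 defers to sponsor safety conventions not included here, so the documents do not show that such a rule is missing.
- **Legacy abatacept subjects not entering the OLE.** Their absence from the legacy list in 7.4.1 might look like a gap. SAP 6.1 defines their period, and the general last-dose-plus-56 bullet in 7.4.1 arguably covers them.

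The reply also notes that no formal comparison is planned on multiple-occurrence events, and that efficacy and the randomised double-blind safety comparison do not use this line. Both are true. Neither reconciles 7.4.1 with 6.1.

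**Conclusion.** SAP 7.4.1 and SAP 6.1 cannot both be followed for this group. The 7.4.1 line is the one to correct: the stated rationale for the 56 days and the other formulas in the section agree with 6.1. On the nominal schedule each affected subject is credited with 28 days too many. That size rests on the two inferences listed in the working, Day 113 for the first Period 2 dose and placebo in Period 2. The mismatch in anchor dates does not depend on either.

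The certain consequence is an overstated cumulative exposure summary for these subjects. A downward bias in the cumulative-period rates of 7.6.4 and 7.6.4.1 is conditional on their using this exposure. The number of affected subjects is not given, so the aggregate effect cannot be determined and may be small. This is a drafting error worth correcting before the end-of-study analysis. It does not threaten the trial's main conclusions.

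**What to change.** In the Period 1 term for legacy subjects on abatacept in Period 1 who entered the OLE (SAP 7.4.1, cumulative abatacept safety period), replace the date of the first Period 2 dose with the date of the last Period 1 dose. The term becomes (last Period 1 dose − first Period 1 dose + 1) + 56, which matches SAP 6.1 and gives 141 days on the nominal schedule. Leave the OLE term as it is.

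The cost is one SAP line and the matching program line. Stated cumulative abatacept exposure becomes slightly smaller, and any rates that use it become slightly higher. Efficacy analyses do not change.
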